7.3. Duration of Participation

Subjects who complete all phases will participate in this study for 33 weeks.

7.4. Test Article(s) (Study Drug(s) and/or Study Device(s))

7.4.1. Description

Experimental cigarettes from the NIDA Drug Supply Program (DSP; FDA Notice Number NOT-DA-13-002) will be used in this study. They are available from the Research Triangle Institute (RTI, North Carolina) with the same additives as commercial cigarettes but have varying levels of nicotine in them. The cigarettes come in either menthol or non-menthol cartons. Each carton includes 10 packs of cigarettes with 20 cigarettes per pack. Each carton is labeled with RTI barcodes, RTI log numbers, and batch/lot numbers. Cigarette packs do not have any labels.

7.4.2. Treatment Regimen

This will be a two-arm randomized double-blinded trial. The study will proceed in four phases.

1. In baseline Phase 1, subjects will smoke their own usual brand of cigarettes for 1 week to get acclimated to study participation.
2. In baseline Phase 2, all participants will then be assigned to use research cigarettes that contain the normal amount of nicotine of conventional store bought cigarettes and matched on the participants' menthol flavor preference (menthol vs. non-menthol) for 2 weeks to get acclimated to smoking research cigarettes. Participants who complete this 2 week period of smoking research cigarettes and want to continue with the study will enter the Randomized Double-Blind Phase.
3. During Randomized Double-Blind Phase 3, participants will be randomized (blinded) to either:
 - a. continue to smoke the usual nicotine content (UNC) cigarettes from Phase 2 for the next 18 weeks
 - b. switch to progressively reduced nicotine content (RNC) cigarettes over the next 18 weeks

Tables 1 and 2 (see above) describe the dosing schedule for those randomized in the Phase 3.

4. Finally, during Treatment Choice Phase 4, both groups will then be offered the choice to:
 - a. return to their usual brand (at their own cost)

- b. Receive assistance to quit smoking (with counseling and FDA-approved medication provided at no cost for 11 weeks).

7.4.3. Method for Assigning Subject to Treatment Groups

Participants will be randomized to one of two experimental conditions based on a pre-determined random number sequence generated by Biostatistics core. Randomization will be stratified by site (Penn State and George Washington University) and by menthol flavor (regular/menthol). This ensures a similar distribution of treatment assignment (1:1 for gradual reduction: control) across study sites to avoid potential confounding.

7.4.4. Subject Compliance Monitoring

Compliance will be monitored throughout the trial by a) daily diary records; b) product accountability logs where the amount of product dispensed will be recorded and unused products collected and recorded; and c) questionnaires administered and clinic visits and during phone calls regarding the use of other tobacco or nicotine products. Participant's confidence in complying with the study protocols will be assessed at each study visit. Any problems that arise or they foresee happening will be discussed and problem-solved with the coordinator.

7.4.5. Blinding of the Test Article

Each carton is labeled with Research Triangle Institute (RTI) barcodes, log numbers, and batch/lot numbers. A packaging slip identifies the nicotine content. An unblinded cigarette administrator will remove all RTI identifiers and replace them with our own blind code labels. The blind code labels will be unique to each carton. The cigarette management software application, developed by the Public Health Sciences Data Management team, will house the blind code number for that carton and its corresponding carton information from RTI.

7.4.6. Receiving, Storage, Dispensing and Return

1. Receipt of Test Article

Experimental cigarettes will be provided free of charge to the investigators via the NIDA Drug Supply Program (see Notice: NOT-DA-13-002). They will be shipped in boxes to Penn State Hershey from the RTI in North Carolina. The boxes will contain cartons of cigarettes- 10 packs in each carton with 20 cigarettes in each pack. Each carton is packaged by nicotine content and menthol (green)/non-menthol (blue) flavoring. Each carton is labeled with RTI barcodes, RTI log numbers, and batch/lot numbers. Individual packs and cigarettes do not have labels.

2. Storage

Cigarettes will be stored in locked standard freezers at Penn State Hershey. Once they are shipped to GWU they will be stored at room temperature. Menthol and non-menthol cigarettes will be stored in separate freezers. The cigarettes will be housed in space utilized for the Investigational Drug Service pharmacy and only the unblinded cigarette administrator and their supervisor will have access to the cigarettes. A service provided by Penn State will monitor and record the temperature of the freezers/fridges.

3. Preparation and Dispensing

Once the cigarettes are received from RTI, they will be blinded as noted above by the cigarette administrator under the supervision of the Investigational Drug Service (IDS) at PSU/HMC. When a person is entered into the cigarette management software application they are randomized to either UNC or RNC cigarettes. The application will use the randomization table provided by the Biostatistics Core to assign participants to either the UNC or RNC group. The application will assign the appropriate carton blind code number to dispense based off of the appropriate nicotine content for that participant. This will allow for a double-blind of the research coordinator and participant. A back up report of the cartons available, blind code, and corresponding nicotine level will be emailed to the cigarette administrator after each randomization so that if the cigarette management application is down we can still manually allocate appropriate cigarettes to a participant. An additional set of blind code labels will be attached to the carton that will be used to place on each cigarette pack in the carton. The labels will include the carton blind code, visit number, and space for participant ID.

4. Return or Destruction of the Test Article

Any unused experimental cigarettes that are returned from the participant will be destroyed according to the general policy for drug disposal of the IDS. A log will be kept on any cigarettes that are destroyed. We will not ship unused experimental cigarettes back to the NIDA Drug Supply Program.

5. Prior and Concomitant Therapy

Concomitant medications will be collected regularly throughout the trial to monitor participant health conditions.

Participants taking smoking cessation medication including bupropion in the prior 3 months will be excluded from the study. Medications related to certain medical conditions that are exclusions to the study, such as COPD and current heart conditions, will serve to alert the study staff of the presence of these conditions during screening. Once the participant is entered into the randomized double blind phase of the study, there are no medications that will interfere with the participant's ability to participate.

8. Data and Specimen Banking

8.1. Data and/or specimens being stored

Participants will be given an option on the consent form that will provide permission for the researchers to bank their biospecimens for future undetermined research projects. Only participants who consent to this option will have their blood, urine, and saliva specimens banked. Specimens will be stored with an ID code attached. The ID code will be associated with their data retained in REDCap. Data retained in REDCap will be stored indefinitely and may be used for future research. The research lab will be using software called Freezerworks to manage the biospecimens.

8.2. Location of storage

Specimens will be stored in the locked research laboratory of [name] on the 3rd floor of the Cancer Institute. All data will be stored in REDCap.

8.3. Duration of storage

Participants that agreed to have their biospecimens banked will be stored indefinitely. REDCap data, data stored in Freezerworks, and any paper records will be stored indefinitely.

8.4. Access to data and/or specimens

The lab manager/technicians, study coordinators, and PI will have access to the freezer room where the specimens will be stored. The lab manager, research assistants, project managers, statisticians, and the PI will have access to the stored data in REDCap.

8.5. Procedures to release data or specimens

Other investigators who are interested in obtaining samples from this project for ancillary studies will first be required to submit a detailed written proposal to [name]. [name] will then take the proposal to the overall Penn State Tobacco Center of Regulatory Science (TCORS) steering committee for review and approval. If the proposal is approved, the investigator will then need to obtain all other regulatory approvals (IRB, departmental scientific committees, etc.) prior to samples being released. Only de-identified data will be released to the investigator. Specimens will only be released if the participant provided written consent to allow their samples to be used by other investigators (this option is included in the original consent form).

8.6. Process for returning results

Investigators will be required to provide a written report on their study results to the TCORS steering committee.

9. Statistical Plan

9.1. Sample size determination

The primary sample size calculation for this project will be based on hypothesis 1a and the main outcome variable is plasma cotinine concentration (measured as ng/ml). The mean value of this continuous variable will be compared between the control group and the experimental group. For plausible effect size and variation, we use results of Benowitz et al [4], where the mean (SD) of plasma cotinine concentration are 240 (120) for the control group and 113 (116) for the experimental group at the 21st week follow-up visit (end of randomization phase for trial). It is expected that the cotinine level in the experimental group is reduced gradually after the randomization and the mean difference of the cotinine level between these two groups at the beginning of the trial for our study will be smaller than the value of 127 ng/ml in Benowitz et al [4]. With a sample size of 70 participants per group, we are able to detect the difference in plasma cotinine concentration level between the two groups as small as 58 ng/ml with at least 80% power (and 68 ng/ml with at least 90% power). In this project we plan to study the mean change of plasma cotinine concentration separately for black and white populations. A total sample size of 280 (70 per group * 2 groups * 2 races) is then needed for this project. We plan to recruit a total of 400 participants for this project by allowing a 30% drop-out rate. The alpha level used for the power analysis is 0.05. Another biomarker of interest is the Glutathione (GSH, measured in μ mol/ml). Within each study population (black or white), a sample size of 70 per

group will enable us to detect a mean difference of GSH of 0.23 with at least 90% power. The common standard deviation is assumed to be 0.40 based on [name] et al (2004). For testing the menthol-by-group interaction effects, our proposed sample size will give us at least 80% power to detect a mean difference of plasma cotinine concentration of 72 ng/ml in the pair-wise comparison of among the group-by-menthol combination (4 levels, alpha is adjusted to 0.0083 by Bonferroni method).

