9.2. Statistical methods

Basic baseline statistics including means (SDs) and frequency distributions (percentages) will be reported for demographic characteristics, subjective and objective measures (such as smoking history, the number of cigarettes and other nicotine products, and smoking topography measures). Where necessary, some characteristics will be reported by the two groups under investigation. Numerical baseline characteristics will be compared between the two groups using two-sample T-test or nonparametric Wilcoxon Rank-Sum test when appropriate. Suitably transformed variables will be used when necessary. Categorical variables will be compared using chi-square tests or Fisher's exact tests. Separate baseline analysis will be done within black and white samples in this study.

To determine the effect of progressive nicotine content reduction (NCR) on cotinine and other biomarkers of smoking exposure in both black and white smokers of lower SES over the 18 week trial period: for each of the biomarkers and other outcome variables of interest, exploratory data analysis will be conducted within each time period and across. Results will be summarized by table and figures (such as boxplots). Profile plots will be generated to show the trajectory of variable across different time periods. The major analytical tool for addressing the specific aims of this study is linear mixed models with repeated measures. For each biomarker and other numerical outcome measures of interest, a linear mixed model for repeated measures will be fit to evaluate the main effects of time, group, and time-by-group interaction; treating baseline scores for outcomes as covariates. Known confounders will be included in the linear models, and other covariates will be included if their individual bivariate associations with both the group variable and outcome are significant at 10% level. The magnitude and direction of the difference between the treatment groups will be quantified by reporting the estimated least-square mean differences at each time point. Separate analysis will be performed in black and white samples individually. We will also test for a number of potential effect modifiers by pooling the trial data of white smokers and black smokers together. Interaction terms that do not reach statistical significance will be dropped from the final model.

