To determine the modifying effect of menthol on progressive nicotine content reduction and biomarkers: modification effects such as the menthol will be examined by incorporating the menthol-by-group interaction in the multi-variable linear mixed model. The three-way interaction of the menthol-by-group-by-time will be explored but will be removed from the model if not significant. If the menthol-by-group interaction were found significant then mean-profile plot will be used to show the interaction in details.

To determine the predictors of participant drop-out/relapse: it is hypothesized that compensatory smoking behavior as measured by smoking topography and expired carbon monoxide, a higher baseline nicotine dependence behavioral score and rapid nicotine metabolism phenotypes will be associated with drop-out/relapse. The status of drop-out/relapse will be combined with the length of time from randomization to drop-out/relapse or loss of follow-up to form a time-to-event type of variable. Participants who completed the randomization phase of study will be considered as censored records. Kaplan-Meier type analysis (for categorical predictors) or simple Cox proportional hazard regression model (for quantitative predictors) will be used to examine the bivariate associations between the possible predictors and time to drop-out. If a predictor has shown marginal significance (with p-value less than 0.10) in the bivariate analysis then it will be kept in the multiple regression analysis. A multi-variable Cox proportional hazard regression

model will be built to examine the effects of the predictors jointly for time to drop-out. The magnitude and direction of effectiveness will be quantified by the estimated hazard ratios with their 95% confidence intervals. The interaction between the predictors will be explored in the analysis but will be removed if not significant.

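### Section 9.1 offers a pairwise two-cell power figure (80% at 72 ng/ml, alpha 0.0083) as power for the menthol-by-group interaction; the term that Section 9.2 tests has no stated power

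*Combined protocol and SAP*

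**What the plan says.** Section 9.1 gives one power statement for menthol. It begins "For testing the menthol-by-group interaction effects, our proposed sample size will give us at least 80% power" and ends with a mean difference of "72 ng/ml in the pair-wise comparison of among the group-by-menthol combination (4 levels, alpha is adjusted to 0.0083 by Bonferroni method"). The evaluable sample behind it is set earlier in the section: "A total sample size of 280 (70 per group * 2 groups * 2 races) is then needed for this project".

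Section 9.2 describes the test for Aim 1b: "modification effects such as the menthol will be examined by incorporating the menthol-by-group interaction in the multi-variable linear mixed model". Two sentences follow. On the three-way term: "The three-way interaction of the menthol-by-group-by-time will be explored but will be removed from the model if not significant". On the two-way term: "If the menthol-by-group interaction were found significant then mean-profile plot will be used to show the interaction in details". No pairwise comparison of the four cells is planned.

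Earlier in 9.2, the general mixed-model paragraph specifies repeated measures, "treating baseline scores for outcomes as covariates", and closes its remarks on effect modifiers with "Interaction terms that do not reach statistical significance will be dropped from the final model".

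Aim 1b in Section 1.1 expects that menthol will not modify the effect on the biomarkers.

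**The concern.** The 9.1 sentence names one test and powers another. A pairwise contrast compares two cell means. The interaction asks whether the treatment difference is the same in menthol and non-menthol smokers, so it uses all four cells. The two can be far apart. If cotinine fell by 127 ng/ml (9.1's reference difference) in both flavors, the treatment contrast within either flavor would be 127 and the interaction would be 0. Power for the first says nothing about the second.

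This matters because the expected result for Aim 1b is a null. A reader who takes 9.1 at its word would believe that a 72 ng/ml modification would be found with 80% probability, and would give a non-significant interaction that much weight.

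The reporting rules add to this. The general rule in 9.2 drops non-significant interactions from the final model. The menthol paragraph states removal only for the three-way term, and a plot of the two-way term only if it is significant. The plan does not say whether the two-way term stays in the model, or whether its estimate and interval are reported, in the very case the aim predicts.

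**Working it through.** **Inputs**
- SDs 120 (control) and 116 (experimental), from 9.1. Each result below is given for SD 120/120, then 120/116.
- 280 evaluable, from 9.1. An even menthol split gives 280/4 = 70 per cell. The split is an assumption. Section 2.3 (menthol preference by race) and the equal race samples in 9.1 make it plausible, and it reproduces 9.1's figure.
- Alpha 0.05 overall, and 0.0083 = 0.05/6 for the six pairs of four cells, from 9.1. Tests are taken as two-sided. Power is from the noncentral t.

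**Step 1. Reproduce 9.1's figure (two cells)**
- SE = sqrt((SDc² + SDe²)/70) = sqrt(28,800/70) = 20.28, or sqrt(27,856/70) = 19.95.
- Difference 72, alpha 0.0083, df 138: power **80.7% / 82.2%**.

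The stated figure of at least 80% reproduces, as a pairwise comparison.

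**Step 2. The interaction on the same basis (one time point, no baseline adjustment)**
- Contrast = (control − RNC in menthol) − (control − RNC in non-menthol).
- SE = sqrt(2 × (SDc² + SDe²)/70) = 28.69 / 28.21, which is √2 times the pairwise SE; df 276.
- Power for 72 ng/ml at alpha 0.05: **70.6% / 72.0%**.
- Detectable interaction at 80% power, alpha 0.05: **80.6 / 79.3 ng/ml**.
- 95% CI half-width: 56.5 / 55.5 ng/ml.
- If 9.1's alpha of 0.0083 were carried over, power would be 44.2% / 45.9%. Nothing in 9.2 applies that alpha to this single term, so alpha 0.05 is the relevant comparison.

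**Step 3. What the planned model could recover** (72 ng/ml, alpha 0.05, even split; every correlation is assumed, because the documents give none)
- *Baseline covariate, one visit.* SE × sqrt(1 − r²), df 275. 80% power needs r = 0.450 / 0.419.
- *Mean of the six post-randomisation visits (Visits 4–9), constant interaction, no baseline covariate.* SE × sqrt((1 + 5ρ)/6), df 276:

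| Between-visit ρ | Power |
|---|---|
| 0.7 | 82.3% / 83.6% |
| 0.8 | 78.2% / 79.6% |
| 0.9 | 74.3% / 75.7% |

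 80% is reached if ρ is at most 0.756 / 0.789.
- *Both together.* SE × sqrt((1 + 5ρ)/6 − r²), df 275:

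| Between-visit ρ | Baseline r | Power |
|---|---|---|
| 0.7 | 0.3 | 87–88% |
| 0.8 | 0.3 | 83–84% |
| 0.9 | 0.4 | 82–83% |
| 0.9 | 0.3 | 79–80% |
| 0.9 | 0.2 | 76–78% |

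 With one common correlation among baseline and all six visits, power is at least 99% whatever its value.

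**Step 4. Sensitivity to the menthol split** (SD 120, one visit, unadjusted, alpha 0.05)
- 70:30: power 63%, detectable interaction 88 ng/ml.
- 80:20: power 52%, detectable interaction about 101 ng/ml.

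Section 7.4.3 stratifies randomisation by flavor but fixes no menthol share.

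**The case against.** The strongest reply is that this is a label, not a wrong number. The 9.1 sentence itself names the pairwise basis, the four levels and the adjusted alpha, and the figure is correct for that contrast. The trial is sized on hypothesis 1a, and the menthol figure drives no design choice. The 71–72% belongs to a single-visit unadjusted test that 9.2 does not plan. With repeated visits and the baseline covariate together, power for 72 ng/ml passes 80% in most plausible settings and falls short only when visits correlate very highly with each other but weakly with baseline. The reporting point is a silence: dropping a term from the final model does not forbid reporting its estimate from the model in which it was tested.

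Much of this stands. The planned model may well have 80% power or more, and nothing here shows otherwise. The 71–72% should be read only as what 9.1's own inputs give for the interaction. The reporting gap is an omission, separate from the mislabelled power.

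Two things remain. Naming the pairwise basis does not supply power for the test named at the start of the sentence. And the recovery depends on correlations, a menthol split and a constant interaction, none of which the plan states; 9.1 takes no such credit.

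**Conclusion.** The concern holds. The power in 9.1 belongs to a two-cell comparison that 9.2 does not plan, and the interaction test of Aim 1b has no stated effect size, alpha or power. The 10-point gap between about 81–82% and 71–72%, and the detectable interaction of 79–81 ng/ml in place of 72, rest on an even menthol split, one time point and no baseline adjustment. A less even split makes both worse; baseline adjustment and repeated visits improve them.

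The conclusion is about what the plan states. It is not a finding that the trial is underpowered for the interaction. On the same unadjusted basis the 95% interval would reach about 56 ng/ml either side of the estimate, against a reference effect of 127 ng/ml, so a non-significant p-value alone would not support absence of modification. The point should be fixed; hypothesis 1a is untouched.

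**What to change.** 1. **Section 9.1.** Relabel the 72 ng/ml figure as a pairwise comparison of two group-by-menthol cells at alpha 0.0083, and add:
 *For the menthol-by-group interaction, 280 evaluable participants give 80% power (two-sided alpha 0.05) to detect about 80 ng/ml, assuming an even menthol split, a single time point and no baseline adjustment.*
 If credit is taken for baseline adjustment or repeated visits, state the assumed correlations and give the figure for the planned model.

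2. **Section 9.2.** Add:
 *The pre-specified two-way menthol-by-group term is exempt from the rule that drops non-significant interactions. The difference in treatment effect between menthol and non-menthol smokers is reported with its 95% CI whatever its p-value. Non-significance alone is not taken as absence of modification.*
 A margin for no modification is optional.

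The cost is two wording changes and one reported estimate with its interval. Sample size, randomisation and conduct stay as they are.
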